The sample consisted of 36 women and 13 men, divided into two age groups: young people between 18 and 30 years old ($22,438 \pm 3,898$) and adults between 31 and 64 years old ($50,212 \pm 9,633$). In terms of origin, 23 were residents of Plasencia (Spain) and 26 in Castelo Branco (Portugal). The descriptive characteristics of the sample are detailed in Table 1.

Table 1. Descriptive characteristics of the sample.

VARIABLES	Total n=49	Origin	Young Men (mean±SD)	Adult Men (mean±SD)	Young Women (mean±SD)	Adult women (mean±SD)
AGE (years)	41,143± 15,485	Spain Portugal	20±2,828 26±NP	46,333±13.317 46,857±10,495	24,111±3,723 19±2	49±9,367 53.50±8.609
	70,545± 12,705	Spain Portugal	80±14,142 69±NP	87,333±17,926 80,714±11,572	68,667±13,684 66,750±8,995	64,411±7,193 66.857±11.016
HEIGHT (m)	1,664±0 ,085	Spain Portugal	1.82±0.113 1.7±NP	1.733±0.025 1.757±0.060	1,652±0.074 1.657±0.049	1.618±0.068 1,616±0.057
	25,404± 3,626	Spain Portugal	24,026±1,280 23,875±np	29,170±6,725 26,148±3,488	25,069±4,334 24,372±3,837	24,611±2,350 25,552±3,548

n: sample size; SD, standard deviation; NP: Not applicable; kg: kilogram; M: Metro; BMI, body mass index; m^2 : Square meter.

Randomization, masking, and experimental design

Participants were randomly assigned to distinct groups using free software Epidat 4.0 (2011, Galicia, Spain). The blinding was double-blind, so that neither the investigators nor the participants knew the group assigned to the participant until the completion of the study and statistical analysis.

The total number of participants was divided into three groups: a control group (T0) (n=12), in which no participants had a skin infection, and two different treatment groups (T1 and T2) (n=37), with diverse levels of EC. The rest of the participants were included in these two treatment groups, including both infected (n=32) and healthy (n=5) participants. Thus, group T1 (n=25) had 23 participants with infection and 2 healthy participants, and group T2 (n=12) had 9 participants with infection and 3 healthy participants.

The clinical evaluation of the participants was carried out before the start of treatment and, subsequently, on days 15, 30, 45 and 60 of treatment, except for cultures, both mycological and bacterial, which were performed at baseline, at 30 days and at 60 days of treatment. All reviews, sampling, and data collected were performed by the same observer.

Choice of EO, base cream, and preparation of treatments

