	East.	Err. East	IC 95%		East.	Err. East	IC 95%	
			Lim. Inf.	Lim. Sup.			Lim. Inf.	Lim. Sup.
Treatment 1%	11.61	2.68	6.36	16.86	-	-	-	-
Treatment 0.5%	14.00	4.04	6.09	21.91	-	-	-	-

Est: statistical survival test; Err. Est: statistician error; CI, confidence interval; Lim. Inf: lower bound; Lim. Sup: upper limit; "-": data not available.

Similarly, to evaluate whether the EO-enriched cream was effective against bacterial infections, the cumulative survival curves for both treatments were plotted (Figure 5). In this case, the treatment curve at 0.5% concentration showed better results than the 1% treatment curve.

[figure not shown]

Figure 5. Cumulative survival curves as a function of the two treatments for bacterial infections.

Thus, the mean time to achieve remission in the T1 group (1%) was 49.35 days, compared to 44.82 days in the T2 group (0.5%) (Table 5). This indicated that the treatment of the T2 group was better, since the infection remitted 5 days earlier on average, although when comparing both treatments using the Long-rank test, no statistically significant differences were found (p -value=0.130). Median survival was 60.00 days for treatment at 0.5%, so half of the participants in the T2 group achieved remission at the end of the study. This value could not be computed for the 1% treatment, indicating that less than half of the subjects in this group experienced resolution of the infection at the end of the trial (Table 5).

Table 5. Mean and mediansurvival time (in days) of remission of bacterial infection for the two EC concentrations.

Group	Media				Median			
	East.	Err. east.	IC 95%		East.	Err. east.	IC 95%	
			Lim. Inf.	Lim. Sup.			Lim. Inf.	Lim. Sup.
Treatment 1%	49.35	2.38	44.68	54.01	-	-	-	-
Treatment 0.5%	44.82	4.38	36.2	53.40	60.0	6.37	47.51	72.49

Est: statistical survival test; Err. Est: statistician error; CI, confidence interval; Lim. Inf: lower bound; Lim. Sup: upper limit; "-": data not available.

Relationship between infections and the rest of the variables analyzed

In relation to hygiene habits, it was found that most of the participants washed their feet daily, used flip-flops in swimming pools or showers, wore breathable footwear and cotton socks, and changed their socks daily (Table 6), although it is true that these habits did not show a statistically significant relationship with respect to the presence or absence of skin infections ($p\text{-value} \geq 0.103$) (Table 7).

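### The Table 5 bacterial remission times are means restricted to 60 days, not average times to remission, and they do not support ranking the 0.5% cream above the 1% cream

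*Combined protocol and SAP*

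**What the plan says.** The subsection on efficacy of treatments, in the Results, gives for bacterial infection: "the mean time to achieve remission in the T1 group (1%) was 49.35 days, compared to 44.82 days in the T2 group (0.5". Table 5 has the rows "Treatment 1% 49.35 2.38 44.68 54.01" and "Treatment 0.5% 44.82 4.38 36.2 53.40" (mean, standard error, 95% limits). The text then concludes: "This indicated that the treatment of the T2 group was better, since the infection remitted 5 days earlier on average". The same sentence goes on to concede that "no statistically significant differences were found (p -value=0.130".

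On medians, the statement for T2, cut here before its last word, is: "Median survival was 60.00 days for treatment at 0.5%, so half of the participants in the T2 group achieved remission at the end of the". The T1 median could not be computed, which the text explains by saying that "less than half of the subjects in this group experienced resolution of the infection at the end of the trial".

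The design section sets the clinical reviews "on days 15, 30, 45 and 60 of treatment", with cultures at baseline, day 30 and day 60 only. The statistical analysis section names the log-rank test for comparing concentrations. Neither that section nor Table 5 states a restriction time for any mean.

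**The concern.** An average time to remission needs a remission time for everyone, or a survival curve that falls to zero. Here the T1 curve is still above one half at day 60, when observation stops. On the text's reading, the T2 curve is at about one half. A Kaplan-Meier mean computed from such a curve is the area under it up to the end of follow-up. It measures average time with infection inside a 60-day window. It cannot exceed 60, however long the remaining infections last.

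Two things are at stake. First, a reader of Table 5 could take the 1% cream to clear bacterial infection in about seven weeks on average, with an upper limit of 54 days, although most of that arm was unresolved at day 60. Second, one concentration is said to be better on a gap that the trial's own standard errors do not separate from zero. The bacterial comparison is also the larger one: by the microbiology results, 19 + 9 = 28 of the 32 infected participants had a bacterial component.

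**Working it through.** **Inputs.** From Table 5: T1 mean 49.35, SE 2.38; T2 mean 44.82, SE 4.38; T2 median 60.0, SE 6.37. From the text: log-rank p = 0.130; T1 unresolved share at day 60, S(60), above 0.5; T2 about 0.5; last visit at day 60.

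**1. Reproduce the printed intervals** (mean ± 1.96 × SE).
- T1: 49.35 ± 4.66 = 44.69 to 54.01 (printed 44.68 to 54.01).
- T2: 44.82 ± 8.58 = 36.24 to 53.40 (printed 36.2 to 53.40).
- T2 median: 60 ± 12.49 = 47.51 to 72.49, as printed. Its upper limit lies beyond the last observation.

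**2. What the means estimate.** True mean = restricted mean to day 60 + S(60) × mean further time after day 60. The second term is positive whenever anyone is unresolved at day 60, and the trial has no data on it. So 49.35 is a lower bound for T1. The same holds for 44.82 if some of T2 was unresolved at day 60, as the text says.

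**3. Difference in restricted means**, with the arms taken as independent.
- 49.35 - 44.82 = 4.53 days (rounded to 5 in the text).
- SE = √(2.38² + 4.38²) = √24.85 = 4.98.
- 95% CI = 4.53 ± 1.96 × 4.98 = -5.2 to 14.3; z = 0.91, two-sided p = 0.36.

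The log-rank p of 0.130 tests a different quantity, so the two p-values need not agree. Neither is below 0.05.

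**4. Does the restriction change the direction?** If both arms had the same mean further time m after day 60, the gap in true means would be 4.53 + (S₁ - S₂) × m. Assume S₂ = 0.50 and m = 30 days. The gap is then 4.8 days at S₁ = 0.51 and 12.0 days at S₁ = 0.75. To reverse it with m = 30 in T1, T2 would need a mean further time of about 40 days, from (4.53 + 0.51 × 30)/0.50, to 54 days, from (4.53 + 0.75 × 30)/0.50. The restriction alone does not turn the ranking round.

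**5. Is p = 0.130 evidence of equal effect?** Event counts are not given. Assuming 10 to 16 remissions and a 9/32 allocation to T2, the power of the log-rank test for a hazard ratio of 2 is about 17% to 24%. A non-significant result is expected even with a sizeable difference.

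**6. What cannot be reconstructed.** If times lay on the 15-day visit grid with no censoring before day 60, the smallest denominator that gives 49.35 is 31 (1530/31), yet T1 has 25 participants. No denominator up to 40 gives 44.82. Early censoring, another way of dating remission, or a unit other than the participant could each explain this, and the document does not say which. The bacterial denominators also conflict: 28 in the microbiology results, 20 in Table 6.

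**The case against.** The strongest reply is that the paragraph discloses most of this. The sentence that ranks T2 first also reports the non-significant log-rank result, which is the planned comparison, and the text says openly that the T1 median was not reached. A mean restricted to 60 days is a legitimate summary. It favours T2, as does the median. On that view only a label is missing.

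The disclosure is real and limits the harm. It does not cure the wording: the text still says that the data indicated T2 was better, and it supports this with an average remission time that was not observed for about half or more of the participants. For fungal infection, a non-significant log-rank result (p = 0.611) is read as similar efficacy. For bacterial infection, a non-significant result sits beside a ranking. Neither reading follows.

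A reader might also infer more than the documents support:
- **That 60 days was too short, or that most T1 infections never remitted.** The document says only that they had not resolved by the end of the trial. A 60-day summary is valid if labelled.
- **That the restriction makes the direction wrong.** Step 4 shows that it does not do so by itself. The ranking fails on precision.
- **That the share still infected can be read off the mean.** If nobody is censored early and all T1 remissions fall on one day, 49.35 implies 17.75% remitted for day 0 (10.65/60), 24% for day 15 (10.65/45) or 36% for day 30 (10.65/30). Table 4 has a T1 fungal mean of 11.61 days, below the first review, so even a floor of day 15 is unsafe.
- **That a constant remission rate gives the true means.** Solving m(1 - exp(-60/m)) = 44.82 gives m of about 98 days and a median near 68 days, against the reported 60.0. That model does not fit the document's own median.

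**Conclusion.** Wrong as written, in two respects. The label is wrong: 49.35 and 44.82 days are mean times with infection restricted to follow-up, and are lower bounds for mean remission time. The ranking is unsupported: the difference is 4.53 days with an approximate 95% CI of -5.2 to 14.3 and log-rank p = 0.130. The point estimate favours T2. The trial shows neither a difference nor equivalence between the concentrations.

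The label finding rests on follow-up ending at day 60 and on the text's own statements about unresolved infections. For T2 it requires that some participants were unresolved at day 60. A median of 60.00 alone would not establish that, but the text says that half had remitted. The interval assumes independent arms, a normal approximation in small groups, and the standard errors of Table 5 taken at face value. If the unit of analysis was not the participant, those standard errors may be too small. The planned test result is unchanged.

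**What to change.** 1. In Table 5 and its text, relabel the means as mean time with infection restricted to 60 days. State that the unrestricted mean cannot be estimated in either arm where participants remained unresolved at day 60.
2. Delete the statement that T2 was better and that its infections remitted 5 days sooner. Replace it with the restricted-mean difference (4.53 days, 95% CI -5.2 to 14.3), the log-rank p-value, and a sentence that no difference between concentrations was shown.
3. Reconcile the bacterial denominators (28 against 20) and state the unit of analysis and how remission was dated.
4. Then report for each arm the number remitted over the number with bacterial infection at days 30 and 60 with exact 95% CIs, the difference between arms with its CI, and the number censored before day 60.

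The cost is a little more reporting from data already held, and a less favourable conclusion.

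### Table 5: the upper confidence limit for the T2 bacterial median (72.49 days) extrapolates beyond the day-60 end of follow-up and should read 'not reached'

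*Combined protocol and SAP*

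**What the plan says.** All references are to the combined protocol and SAP.

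- **Schedule** (section 1, Randomization, masking, and experimental design). Clinical evaluation takes place at baseline and "on days 15, 30, 45 and 60 of treatment". Cultures are the exception, "which were performed at baseline, at 30 days and at 60 days of treatment". Nothing is scheduled after day 60.
- **Group size** (same section): "group T2 (n=12) had 9 participants with infection and 3 healthy participants". The number of T2 participants with bacterial infection is not given.
- **Result** (section 2, Efficacy of treatments, Table 5). The T2 median, standard error and 95% limits are "60.0 6.37 47.51 72.49". The text reads the median as half of T2 being in remission at study end: "Median survival was 60.00 days for treatment at 0.5%, so half of the participants in the T2 group achieved remission".
- **The 1% group** (same section). No median is given: "This value could not be computed for the 1% treatment, indicating that less than half of the subjects in this group experienced resolution".
- **Comparison of the groups** (same section). It rests on the log-rank test: "no statistically significant differences were found (p -value=0.130").
- **Method** (section 1, Variables and statistical analysis). Cox regression and the log-rank test are named. No method is stated for the confidence interval of a median survival time.

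**The concern.** A normal-theory interval for a median needs the slope of the survival curve around the median. Here the median falls on the last scheduled visit, so nothing is observed to its right, and the group is very small. A symmetric interval in that position must place half its width where there are no data.

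What is at stake is the precision attached to a reported efficacy figure. Since no method is stated, a reader will take the interval at face value: the median time to bacterial remission on 0.5% cream is known to within about 12.5 days and lies below 73 days with 95% confidence. The data cannot support an upper bound of that kind.

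**Working it through.** **Inputs.** Median 60.0, standard error 6.37, limits 47.51 and 72.49 (Table 5). End of follow-up day 60, T2 n = 12, of whom 9 infected (section 1). Not given: the bacterial number in T2, the event times and the censoring.

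**Step 1. Reproduce the printed interval.** Estimate ± 1.96 × SE, with 1.96 × 6.37 = 12.485:

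- lower: 60.0 − 12.485 = 47.515 (printed 47.51)
- upper: 60.0 + 12.485 = 72.485 (printed 72.49)

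The agreement is within rounding of the SE. The T2 mean in the same table follows the same formula: 44.82 ± 1.96 × 4.38 = 36.24 to 53.40 (printed 36.2 to 53.40). So the median's interval is a symmetric normal one, with no sign of a computing or transcription error. The value 6.37 itself cannot be verified without the event times.

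**Step 2. Distance past follow-up.** 72.49 − 60 = 12.49 days.

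**Step 3. What a test-inversion interval would give.** A Brookmeyer-Crowley upper limit is the first time at which the upper 95% limit of the survival curve S(t) falls below 0.5. It is finite only if the upper limit of S(60) is below 0.5. I assume complete follow-up and, following the text, about half of the group unresolved at day 60. The limits used are:

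- plain: S + 1.96 × √(S(1 − S)/n)
- log-log: S raised to the power exp(−1.96 × v), with v = √((1 − S)/(nS)) / |ln S|
- exact: Clopper-Pearson

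Worked for 4 of 9 unresolved (S = 0.444):

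- plain: 0.444 + 1.96 × 0.1656 = 0.769
- log-log: v = 0.3727/0.8109 = 0.460, exponent exp(−0.901) = 0.406, limit 0.719

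| Assumed n | Unresolved at day 60 | Exact | Plain | Log-log |
|---|---|---|---|---|
| 5 | 2 | 0.853 | 0.829 | 0.753 |
| 6 | 3 | 0.882 | 0.900 | 0.804 |
| 7 | 3 | 0.816 | 0.795 | 0.734 |
| 8 | 4 | 0.843 | 0.846 | 0.775 |
| 9 | 4 | 0.788 | 0.769 | 0.719 |
| 10 | 5 | 0.813 | 0.810 | 0.753 |
| 11 | 5 | 0.766 | 0.749 | 0.707 |
| 12 | 6 | 0.789 | 0.783 | 0.736 |

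Nine is the ceiling implied by the infected count. Twelve is the whole T2 group, as an outer case. Every value exceeds 0.5, so the upper limit is 'not reached' throughout.

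**Step 4. What would make the limit finite.** At n = 9, at most 1 unresolved (exact and log-log) or 2 (plain). At n = 12, at most 2 (exact and log-log) or 3 (plain). Both are well below half. Even then the limit would be an observed event time no later than day 60, so this method could not return 72.49.

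**Step 5. The means.** If about half of T2 and more than half of T1 were unresolved at day 60, the means 44.82 and 49.35 can only be areas under the curves up to the end of follow-up. Table 5 does not label them as restricted.

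**The case against.** The strongest defence is that the interval concerns the underlying median, which can exceed 60 days because some participants had not resolved when observation stopped. This stands. A reader might infer that the interval is invalid because it passes day 60, but that does not follow. It agrees with its own standard error and is a weak large-sample approximation. The narrower criticism survives: a finite limit of 72.49 has no data behind it.

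Three other inferences are tempting and are not supported.

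- **That the lower limit of 47.51 is wrong because no culture was taken then.** A confidence limit need not fall on an assessment day. Without event times the lower limit cannot be recomputed in either direction.
- **That the median is known only to lie between days 30 and 60.** This assumes bacterial remission was timed by culture alone. The documents do not define the remission date. Clinical reviews, with Wood's light, also took place at days 15 and 45. The fungal means of 11.61 and 14.00 days in Table 4 could not arise if every recorded time were 30 days or later.
- **That the contrast between T2 and T1 depends on this interval.** The text never cites 47.51 to 72.49. It uses the point estimate, the means and the log-rank test, none of which a better interval alters.

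It is also fair to say that 9 counts any T2 infection (fungal, bacterial or mixed), so it is a ceiling for the bacterial analysis and not its sample size.

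**Conclusion.** The concern holds as a reporting correction to one efficacy figure. The T2 bacterial median has a symmetric normal interval whose upper limit is 12.49 days past the end of follow-up. It should be shown as not reached.

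This rests on two assumptions: complete follow-up to day 60, and about half of T2 unresolved by then. The second comes from the text's own reading. A median of 60 alone says only that at least half had remitted by that day. Under these assumptions the upper limit for the proportion unresolved is 0.72 to 0.79 at n = 9 or 12, and 0.71 to 0.90 over all n from 5 to 12.

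The median of 60.0, the missing T1 median and the finding of no significant difference between concentrations (p = 0.130) all stand.

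**What to change.** 1. In Table 5, replace the T2 median's interval with a Brookmeyer-Crowley interval on the log-log scale. Print 'not reached' for any limit at which the band does not cross 0.5, and name the method under Variables and statistical analysis.
2. Give the number with bacterial infection in each group and the numbers at risk at each visit.
3. Add the day-60 remission proportion with an exact 95% interval for both groups. Day 60 is both a clinical and a culture visit, so this does not depend on how remission was timed between visits. As an illustration with assumed counts, 5 of 9 gives 21% to 86% and 6 of 12 gives 21% to 79%.
4. Label the means 49.35 and 44.82 as restricted to 60 days.

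The cost is a re-run on existing data and a table edit, with no new data. The downside is a wider, open-ended interval.

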A skin sample was taken following the standard procedure described for the diagnosis of mycosis (5). The epithelial surface was disinfected with 70° alcohol and a sample was collected from the affected area by scalpel scraping. Subsequently, the sample was analyzed using two different procedures. The 30% KOH test (35.3g/100ml distilled water) (Labbox, Barcelona, Spain) followed by conventional light microscopy observation to identify the infective fungal agent, and microbiological culture on Sabouraud dextrose agar with chloramphenicol and cycloheximide (Condalab, Torrejón de Ardoz, Madrid), at a constant temperature (between 25°C and 28°C) for 2 to 4 weeks, in order to inhibit molds and bacteria and observe the growth of the infective fungal agent. Participants with infection were considered to be those who had positive results in both tests, excluding cases in which only one test was positive.

- Bacteriological culture

A skin sample was taken following the standardized procedure for microbiological analysis (6). The skin was disinfected with 70° alcohol and a sample was taken by smear with a sterile swab from the affected surface. Again, the analysis was carried out using two distinct and independent procedures. A Gram stain was performed to identify bacteria and the sample was inoculated with Sabouraud dextrose broth (SDA) (Merck, Germany), at a constant temperature (between 27°C and 31°C) for 1 to 3 days. Participants with infection were considered to be those who had positive results in both tests, excluding cases in which only one test was positive.

Variables and statistical analysis

The following variables were analyzed: sociodemographic (sex and age), anthropometric (weight, height, and BMI), hygiene-related habits (frequency of foot washing, use of flip-flops in showers/pools, type of footwear and socks and frequency of sock change), presence or absence and type of infection, degree of hydration and concentration of EC group T0 (0%), group T1 (1%) and group T2 (0.5%). Of these variables, age, weight, height, BMI, and hydration were considered quantitative compared to the rest that were analyzed as qualitative.

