Statistical analysis was performed using the statistical analysis program IBM-SPSS Statistics for Windows version 25 (IBM Corp. Armonk, NY, USA). Some figures have been obtained using the Python programming language, using the Seaborn library (Waskom, M. L., (2021). Seaborn: statistical data visualization. *Journal of Open-Source Software*, 6(60), 3021, <https://doi.org/10.21105/joss.03021>).

Normality was assessed using the Shapiro-Wilk test. To evaluate the influence of different variables on infection remission, a Cox regression model was used, and survival curves of significant factors were plotted. To compare the efficacy of different EC concentrations, survival curves were compared using the Log-rank test. The Mann-Whitney U test was used to assess hydration averages according to sex. To check if there were improvements in hydration due to the use of the cream with different concentrations of EC (T1 and T2) compared to the control group (T0), hydration levels were compared using Kruskal-Wallis tests, using the Mann-Whitney U test with correction of p-values by the Bonferroni method for multiple comparisons.

In all statistical tests, significance was considered when p-value<0.05 and high significance when p-value<0.01.

2. Results

Analysis of the Elemental Composition of Commercial S. S.

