The determination of the specific composition of the 3 types of EO made it possible to quantify the exact concentration of the different components of each of the EO, choosing the EO with the highest concentration of components with antimicrobial activity and the lowest concentration of components susceptible to interaction with other drugs or to produce allergies in the participant, such as terpinolene, alpha-terpinene and sabinene and the aged components of EO(7-10). Specifically, the main component in the 3 EO samples was terpinen-4-ol, with a concentration between 28.47% and 29.15%, followed by gamma-terpinene and alpha-terpinene (Table 2). These three components accounted for approximately 65% of the total EO in the 3 samples analyzed. On the other hand, alpha-terpineol and eucalyptol were found to be the fourth and fifth most concentrated components, with percentages between 3.85%-5.85% and 4.12%-5.81%, respectively. These two, along with m-cymene, alpha-pinene, and terpinolene, made up about 24% of the total EO. The rest of the EO was made up of up to 22 different compounds with minority percentages, considered together as traces. For all the above results, the EO of *M. alternifolia* of the brand Esencias Lozano® was used, since it was the EO that presented the highest percentage of the components of terpinen-4-ol, eucalyptol and alpha-terpineol, whose antimicrobial activity has been described in the bibliography(7,11-14).

Table 2. Percentages of the different components according to the EO studied in the CG-MS.

Components	Trademarks of EO		
	Naissance®	Marnys®	Esencias Lozano®
Terpinen-4-ol	28.47%	29.10%	29.15%
Gamma-terpinene	21.92%	20.42%	22.86%
Alpha-Terpinene	13.10%	11.23%	13.58%
Alpha-terpineol	3.85%	4.03%	5.85%
Eucalyptol	4.12%	4.82%	5.81%
M-cymene	3.40%	5.28%	4.96%
Alpha-pinene	3.18%	3.15%	5.12%
Terpinolene	4.65%	4.26%	3.72%
Traces	17.31%	17.71%	8.95%
Total	100%	100%	100%

®: trademark; %: percentage of the component in the sample.

Test results for microbiological diagnostics

After reading the tests performed for microbiological diagnosis, it was determined that, of the 49 total participants, 32 (65.3%) were positive for skin infections. Of these 32 participants, 4 (12.5%) had fungal infection, 19 (59.4%) showed bacterial infection, and 9 (28.1%) had mixed fungal and bacterial infections simultaneously.

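### The remission analyses are not restricted to participants infected at baseline with the organism analysed; Table 4 appears to count uninfected records as day-0 remissions, and the at-risk set of Table 5 cannot be determined

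*Combined protocol and SAP*

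**What the plan says.** The section on randomization, masking and experimental design puts uninfected people in both oil arms: "group T1 (n=25) had 23 participants with infection and 2 healthy participants" and "group T2 (n=12) had 9 participants with infection and 3 healthy participants". Together the oil arms are described as "including both infected (n=32) and healthy (n=5) participants", and the control group has no infected participants. The microbiology results split the 32 infected: "4 (12.5%) had fungal infection, 19 (59.4%) showed bacterial infection, and 9 (28.1%) had mixed fungal and bacterial infections simultaneously".

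Infection status has a rule: "Participants with infection were considered to be those who had positive results in both tests". Remission has none. The section on variables and statistical analysis names Cox regression for factors influencing remission and adds "To compare the efficacy of different EC concentrations, survival curves were compared using the Log-rank test". It gives no analysis set, event definition, censoring rule or unit of analysis.

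Clinical reviews took place "on days 15, 30, 45 and 60 of treatment". Cultures were repeated only on days 30 and 60.

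Under Efficacy of treatments, Table 4 reports mean fungal remission times of 11.61 days (T1) and 14.00 days (T2) with log-rank p=0.611. The text says that all fungal infections had resolved by day 30 and that the two concentrations are similarly effective. Table 5 reports bacterial means of 49.35 and 44.82 days (p=0.130). The text calls T2 better. From its median of 60 days it infers "so half of the participants in the T2 group achieved remission at the end of the study", and from the missing T1 median that fewer than half of T1 resolved. Neither table gives numbers at risk or events.

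**The concern.** Only a person who carried the organism at baseline can clear it. Anyone else must be left out, counted as remitted at once, or counted as never remitted, and the documents do not say which. Counting them as instant remissions shortens the reported times; counting them as never remitted lengthens them. If their share differs by arm, the comparison moves as well.

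The control group had no infections, so 1% against 0.5% is the only between-group efficacy comparison the trial can make. At stake are the fungal remission times, the conclusion of similar fungal efficacy, and the stated bacterial advantage of T2.

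**Working it through.** **Who could be scored.**
- No infection: 2/25 = 8% of T1, 3/12 = 25% of T2, 5/37 overall.
- Any bacterial infection: 19 + 9 = 28, so 37 − 28 = 9 of 37 (24%) had none.
- Any fungal infection: 4 + 9 = 13, so 37 − 13 = 24 of 37 (65%) had none.

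**Table 4 against the schedule.** People infected at baseline and first reassessed on day 15 (review) or day 30 (culture) cannot average 11.61 or 14.00 days. Some records must carry earlier times.

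**Reproducing Table 4.** Suppose n records per arm, d of them remissions on day 0, and all other remissions on day 30.
- Mean = 30 × (n − d)/n. T1: 30 × 12/31 = 11.61. T2: 30 × 7/15 = 14.00. Both as printed.
- Variance = mean² × d/[n(n − d)] × m/(m − 1), with m the total number of events.
  - T1, m = 25: 11.613² × 19/(31 × 12) × 25/24 = 7.175, SE 2.68, limits 6.36 to 16.86.
  - T2, m = 12: 14² × 8/(15 × 7) × 12/11 = 16.29, SE 4.04, limits 6.09 to 21.91.
  - All as printed. With every record an event (m = 31 and 15), the SEs would be 2.67 and 4.00.
- Log-rank. If all records still at risk on day 30 remit then, day 30 adds nothing and only day 0 counts. Observed in T1: 19. Expected: 27 × 31/46 = 18.196. Variance: 27 × (31/46) × (15/46) × (19/45) = 2.505. Chi-square = 0.804²/2.505 = 0.258, p = 0.611, as printed.

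The three results fit together if 31 − 25 = 6 records in T1 and 15 − 12 = 3 in T2 are censored before day 30. If those records were instead censored on day 30, p would be 0.799.

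Under this reconstruction, 61% of T1 records (19/31) and 53% of T2 records (8/15) are day-0 events. The whole difference between 11.61 and 14.00 days comes from those two fractions, because every other remission falls on day 30. The event totals, 25 and 12, equal the numbers of people in T1 and T2, although only 13 people had a fungal infection.

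**What does not tally.** The 31 + 15 = 46 records exceed 37 people. The 19 + 8 = 27 day-0 records exceed the 24 people without fungal infection. Table 6 counts 20 bacterial and 8 fungal infections, against 28 and 13 above.

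**Table 5.** The T1 mean and SE fit 31 records with 8 events on day 30, 6 on day 45, 17 censored on day 60 and none on day 0:
- mean = 60 − (8 × 30 + 6 × 15)/31 = 49.35;
- SE = √{225 × [38/31 − (22/31)²]/31 × 14/13} = 2.38, where 38 = 8 × 2² + 6 × 1² and 22 = 8 × 2 + 6 × 1.

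The lower limit comes out at 44.70 against 44.68 printed. No pattern of plausible size was found for the T2 row. So the table does not reveal its denominators.

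The share with no bacterial infection depends on where the 4 fungal-only participants sat. If all were in T1 it is 6/25 = 24% against 3/12 = 25%. If all were in T2 it is 2/25 = 8% against 7/12 = 58%. The arm imbalance is therefore anywhere from 1 to 50 percentage points.

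If half of T2 is read as 6 of 12, and all 9 infected are taken as bacterial, clearance among the infected is 3/9 if the 3 healthy count as remitted and 6/9 if they count as not remitted.

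**The case against.** The captions speak of remission of infection, so an infected-only analysis is a natural reading. The statement that half of T2 remitted is inferred from a Kaplan-Meier median, so its denominator is whoever was in that curve. The reference to the T2 group may be loose wording. This stands for Table 5: a reader might infer that the T2 share was taken over the wrong denominator of 12, and the documents do not show that.

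A reader might also infer from 8% against 25% healthy that the bacterial comparison is biased towards T2 by a calculable number of days. That is not supported either. The 4 fungal-only participants also had no bacterial infection, their arm is not given, and the T1 row is compatible with no day-0 events at all.

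Both comparisons are reported as non-significant, so no claim of statistical significance is at risk. What is exposed is the fungal times, the similarity conclusion and the wording on bacterial direction.

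For Table 4 the infected-only reading does not survive the schedule, because means below 15 days are impossible on it. Undocumented interpolation of remission times is the other explanation, and it too would need to be stated.

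**Conclusion.** The concern holds. No at-risk set is defined, although 24 of 37 oil-arm participants could not be scored for fungal remission and 9 of 37 could not be scored for bacterial remission.

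For fungal infection the printed results appear to rest largely on day-0 records: 19 of 31 and 8 of 15. If so, the stated times and the similarity conclusion say little about clearance in infected people. This assumes event times only at baseline and on scheduled days, the m/(m − 1) variance factor, and 6 and 3 records censored before day 30. The agreement is close, but it is not proof that uninfected people were scored as instant remissions, and the record counts do not map onto the stated infection counts.

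For bacterial infection the at-risk set cannot be determined. The half, fewer-than-half and better statements cannot be read as clearance among the infected, and no size or direction of bias can be assigned.

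**What to change.** In the section on variables and statistical analysis:
- Define remission, and limit each Kaplan-Meier, log-rank and Cox remission analysis to participants positive for that organism type at baseline. Keep the 5 healthy oil-arm participants for hydration only.
- Use one record per participant, or state the unit and account for clustering.
- Date events at scheduled assessments and state the censoring rule.

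In the results:
- Reconcile the microbiology counts (28 bacterial, 13 fungal) with Table 6 (20 and 8); the baseline-positive set is undefined until this is done.
- Rerun Tables 4, 5, 8 and 9, with number at risk, events and censored per arm.
- Replace the half and fewer-than-half statements with x/n remitted by day 60 among the baseline-positive, by arm, with exact confidence intervals.

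Cost: no new data collection, but the source records must be checked because the unit of analysis is unclear. The sets will be smaller (at most 23 in T1 and 9 in T2 if the unit is the participant) and the intervals wider. If Table 5 was already restricted, stating so with its counts settles that part.
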